13 APPENDICES

Confidential Page 43 of 50

Appendix 1. Schedule of Assessments and Procedures

Activities	Screen	Clinic Visit 1	Home Visits			Clinic Visit 2	Home Visit	Home Visit	Home Visit	Clinic Visit 3	Clinic Visit 4	Discon Visit ^b
Visit window Days (D)	≤7 days before Day 1	Day 1 ^a	Wk 1 D 7	Wk 2 D 14	Wk 3 D 21	M 1 D 28	Wk 4 D 35	Wk 5 D 42	Wk 6 D 49	D 56 M 2	D 90 M 3	
		± 0	± 1	± 1	± 1	± 1	± 2	± 2	± 2	± 2	± 2	
Informed consent (while in hospital) ^c	X											
Check inclusion and exclusion criteria /verify eligibility ^d	X	X										
Demographic characteristics	X											
Obtain estimation of socioeconomic status after enrollment		X										
Record medications for infant	X	X	X	X	X	X	X	X	X	X	X	X
Record antibiotics/probiotics taken by mother	X	X	X	X	X	X	X	X	X	X	X	X
Anthropometric measurements ^e , bilateral pedal edema	X	X				X				X	X	X
Full medical history f, full PE f, VS, and L and W	X											
Interim history ^g , focused PE ^g as necessary, VS, L, and W		X				X				X	X	X
Randomization (at hospital discharge)		X										
Collect engraftment stool sample		X				X				X	X	
Collect exploratory stool samples h		X				X				X		
Collect serum samples h		X				X						
Provide a week's worth of doses for daily administration i		X	X	X	X							
Bi-26/placebo for daily administration ^j		X	X	X	X	X						
Record all AEs and SAEs	X	X	X	X	X	X	X	X	X	X	X	X
Provide feeding and dosing diary/review contents with parent(s)/legal guardian		X	X	X	X	X	X	X	X	X	X	
Record number of doses used from diary			X	X	X	X						X

Confidential Page 44 of 50

Record feeding history (number of feedings that are from breastmilk, and from other source/s) from diary ^k		X	X	X	X	X	X	X	X	X	X
Record dose storage information		X	X	X	X						X
Sub-study activities ¹ : • Place box with temperature data logger in the home refrigerator						X					
• Collect box with temperature data logger from the home refrigerator								X			

D = day; Wk = week, M = month; AE = adverse event; L = infant's length; PE = physical examination; VS = vital signs; W = infant's weight

Approximately 20% of the participants at each site will be enrolled into the sub-study. Boxes with a temperature data logger will be placed in the home refrigerators at the participants' homes and collected after 2 weeks. The study staff will return the box to the clinic so the information from the temperature data logger can be uploaded.

^a All-study assessments related to determination of the participant's health (medical history, PE, VS, L and W, anthropometric measures, bilateral pedal edema) and collection of all study samples should occur prior to administration of the study intervention.

b Discon visit = A discontinuation visit will be scheduled, whenever possible, for participants who discontinue or withdraw from the study.

^c Informed consent and the screening visit may occur the same day as enrollment and randomization (Day 1). Study assessments should not be duplicated for visits completed on the same day. Participants who are out of window due to a change in expected discharge date, may be rescreened, if applicable.

d Enrollment will occur on Day 1 after all eligibility criteria have been verified. Record whether discharged to home or nutritional rehabilitation unit at Visit 1.

^e Anthropometric measurements: WAZ, weight-for-length z score (WLZ), mid-upper arm circumference (MUAC), head circumference, and skinfold thickness.

^f Refer to Protocol Section 8.3.1 full medical history and full PE.

^g Refer to Protocol Section 8.3.2 for interim medical history and focused PE.

^h Samples to measure exploratory biomarkers will be collected.

¹Doses to be delivered within 2 days before planned use to ensure no break/no delay in dosing regimen.

^j Monitor infants for 30 minutes after dosing, and a repeat dose will be administered if infant vomits within this observation period. If the daily dose is administered at the clinic during a visit, steps should be taken to ensure that blinding is maintained by not having any study personnel present during reconstitution and dose administration.

^k The dosing information described in Protocol Section 6.4 (Feeding history) should be recorded in the diary from Day 1 through Day 28.

¹ Participants' parent/legal guardian will be asked if they agree to participate in this sub-study and consent obtained at the enrollment visit.

Appendix 2. Imputation of Partial Dates

Table 6. Imputation Rules for Partial Dates – Adverse Events

Table 0.	1						
Parameter	Missing	Additional Condition	Imputation				
Start Date	D only	M and Y are prior to first study intervention dose	First day of indicated month				
		M and Y is same as first study intervention dose	Date of first study intervention dose				
		M and Y are after first study intervention dose	First day of indicated month				
	M and D	Y is prior to first study intervention dose	01 Jan of indicated year				
		Y is same as first study intervention dose	Date of first study intervention dose				
		Y is after first study intervention dose	01 Jan of indicated year				
	M, D, and Y	-	assumed to be TEAE				
End Date	D only	M and Y are prior to last study intervention dose	Last day of indicated month				
		M and Y is same as last study intervention dose	Date of last observation				
		M and Y are after last study intervention dose	First day of indicated month				
	M and D	Y is prior to last study intervention dose	31 Dec of indicated year				
		Y is same as last study intervention dose	Date of last observation				
		Y is after last study intervention dose	01 Jan of indicated year				
	M, D, and Y	-	TEAE is ongoing				
	-	Estimated end date is before a complete or imputed AE start date	Last day of the month of AE start date				

D = day; M = month; Y = year; TEAE = treatment-emergent adverse event

Note: The imputation of end date must be later than start date

Table 7. Imputation Rules for Partial Dates – Prior and Concomitant Medications

Parameter	Missing	Additional Condition	Imputation
Start Date	D only	M and Y same as M and Y of first study intervention dosing	Date of first study intervention dose
		M and/or Y not the same as M and Y of first study intervention dosing	First day of indicated month
	M and D	Y same as Y of first study intervention dosing	Date of first study intervention dose
		Y not the same as Y of first study intervention dosing	01 January of indicated year
	M, D, and Y	none - date completely missing	Date of first study intervention dose
End Date	D only	M and Y same as M and Y of last study intervention dosing	Date of last study intervention dose
		M and/or Y not the same as M and Y of last study intervention dosing	Last day of indicated month
	M and D	Y same as Y of last study intervention dosing	Date of last study intervention dose

Confidential Page 46 of 50

Statistical Analysis Plan: Gates MRI-MNK01-301	Gates MRI
Bi-26	Initial draft
Y not the same as Y of las intervention dosing	t study 31 December of indicated year

M, D, and Y none – date completely missing Date of last study intervention dose

M, D, and Y D = day; M = month; Y = year

Confidential Page 47 of 50

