5.1. Inclusion Criteria

Participants are eligible to be included in the study only if all of the following criteria apply:

Age

1. Participant must be between 30 days and 120 days of age (inclusive), at the time of enrollment (study Day 1)

Type of Participant and Disease Characteristics

- 2. Hospitalized for acute non-surgical illness
- 3. Completed acute stabilization phase of treatment, including fluid rehydration and antibiotic course, prior to enrollment (study Day 1)

Weight

4. WAZ at enrollment (study Day 1) is less than negative 2 (<-2)

Sex

5. Any

Informed consent

6. Participant's parent(s)/legal guardian is capable of giving informed consent which includes agreement to comply with the requirements and restrictions listed in the informed consent form (ICF) and in this protocol

Additional requirements

- 7. Participant's parent(s)/legal guardian agrees to stay in contact with the study site for the duration of the study, provide updated contact information as necessary, and have no current plans to relocate from the study area for the duration of the study
- 8. Participant's parent(s)/legal guardian has easy access to reliable refrigeration (for storage of investigational product)
- 9. Participant receives some feedings from breastmilk and mother intends to continue breast-feeding.

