11.3 Prior and Concomitant Medications and Procedures

A prior medication is defined as having started and ended prior to first dose of study intervention. A concomitant medication is defined as either having started prior to first dose of study intervention and ended on/after first dose of study intervention, is ongoing at Baseline or, having started on/after first dose of study intervention. Medications will be coded by site of action and therapeutic and clinical characteristics using WHO's ATC Classification.

The number and percentage of participants reporting prior and concomitant medications will be summarized separately by ATC Class and preferred name, by treatment group and overall.

The same table will be presented for concomitant medications for the mothers of the participants.

The following ATC class/terms for probiotics and antibiotics will be used to identify the participants for the subgroup analysis based on infant concomitant antibiotic/probiotic use (see Section 8.2):

- A07FA01 Lactic acid producing organisms (probiotics).
- A07FA02 Saccharomyces boulardii (probiotics).
- A07FA51 Lactic acid producing organisms, combinations (probiotics).
- J01 (antibiotics).
- J04 (antibiotics).

Prior/concomitant status (according to the definition provided at the start of this section) will be derived using the medication start and stop dates. For partial dates, see imputation rules in Appendix 2.

Reason for use, dates of administration including start and end dates, dosage information including dose and frequency of any medication or vaccine (including over-the-counter or prescription medicines, vitamins, and/or herbal supplements) that the participant was receiving at the time of screening or received during the study will be presented in participant listings for infants and mothers.

All procedures will be classified according to the latest version of MedDRA. The number and percentage of participants reporting concomitant procedures will be summarized separately by SOC and PT, by treatment. Concomitant procedures are defined as having been performed on or after the date of the first dose of study intervention. Procedures will be presented in a participant listing. The listing will include the start and stop dates of the procedures, whether it is related to an AE, reason for procedure, interpretation of procedure and findings.

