11.6.1 Adverse Events

Safety assessments include SAEs and AEs from the time the ICF is signed through Day 90 (or at the date of last visit/study discontinuation).

An AE is considered treatment emergent if it started on or after the date of first dose of study intervention administration.

Confidential Page 37 of 50

An AE overview table containing the number and percentage (expressed in percent) of participants with AEs from Day 1 through Day 90 will be summarized by treatment group for the following:

- Any AE
- Any TEAE
- TEAEs related to study intervention
- TEAEs by maximum severity (Mild, Moderate and Severe)
- TEAEs leading to study intervention discontinuation
- TEAEs leading to study withdrawal
- Serious TEAEs
- Serious TEAEs with Outcome of Death

Additionally, the number and percentage of participants with AEs will be provided by SOC and PT and by treatment group for the following:

- Any TEAE
- TEAEs by maximum severity
- TEAEs related to study intervention
- Serious TEAEs
- Serious TEAEs related to study intervention

By-period summaries will be presented for TEAE and serious TEAEs by treatment group, where period is defined as in Section 10.1.

The overall AE summary table, AE table by SOC and PT and SAE table by SOC and PT will be presented by subgroups as specified in Section 8.2.

All AEs and SAEs will be classified according to the latest version of MedDRA.

SOC and PT will be sorted alphabetically by SOC and by decreasing frequency of preferred term in the all Bi-26 group (then alphabetically for ties). If a participant has more than one AE at a given level (eg, SOC and preferred term), the participant will only be counted once within that level. All summary tables will include the number of AEs. Missing severities and relationship will not be regarded as 'worst case'.

The following listings will be presented:

- All AEs through to Day 90
- SAEs through to Day 90

The AE listing by participant will display all reported AEs up to Day 90 and will include the verbatim term in addition to the SOC and preferred term. This listing will also include all relevant data associated with the event: eg, date of onset, date resolved, date of first dose, date of last dose, severity, whether AE is serious, outcome, relationship to study intervention, action taken with study intervention, and required therapy. When a date is presented, the study day

Confidential Page 38 of 50

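### SAP Appendix 2 moves partial start dates to the first-dose date without checking a known end date, so treatments and events that ended before dosing count as concomitant or treatment-emergent

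*SAP*

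**What the plan says.** Appendix 2 of the SAP has one table of partial-date rules for adverse events (Table 6) and one for prior and concomitant medications (Table 7).

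- **Day missing.** In Table 6, when "M and Y is same as first study intervention dose", the start is imputed as "Date of first study intervention dose". Table 7 has the same rule under the condition "M and Y same as M and Y of first study intervention dosing".
- **Month and day missing.** In both tables, if the year is that of the first dose, the start again becomes the first-dose date.
- **Whole date missing.** Table 6 says the event is "assumed to be TEAE". Table 7 uses the first-dose date.
- **Order of dates.** Table 6 has one row for dates out of order, headed "Estimated end date is before a complete or imputed AE start date". It moves the end date later. The footnote to Table 6 also concerns only imputed end dates. Table 7 has neither.

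These imputed dates decide classification. SAP 11.6.1 states: "An AE is considered treatment emergent if it started on or after the date of first dose". SAP 11.3 states: "A prior medication is defined as having started and ended prior to first dose of study intervention". Under the same section, a start on or after the first dose is enough to make a medication concomitant, and partial dates are referred to Appendix 2.

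**The concern.** A known end date before the first dose settles the question that the imputation is meant to answer: whatever the start was, it came no later than the end. The tables ignore that information and assign a start that falls after the recorded end.

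The design makes such records likely for medications. Inclusion criterion 3 (Protocol 5.1) reads: "Completed acute stabilization phase of treatment, including fluid rehydration and antibiotic course, prior to enrollment (study Day 1". Exclusion criterion 8 (Protocol 5.2) bars infants still on antibiotics. A finished course with a stop date before dosing is thus what the plan expects to see. If its start is partly or wholly unknown, it can be counted as antibiotic exposure during the study.

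The flag for infant concomitant antibiotic or probiotic use through Day 56 is then used in three places: as a subgroup (SAP 8.2), as a split of the adverse event tables (SAP 11.6.1), and as a candidate confounder in the adjusted sensitivity MMRM (SAP 11.5.2.4.2). Counting a completed hospital course as use after dosing blurs the contrast that the flag is meant to draw.

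**Working it through.** The plan states no figure on this point, so there is none to reproduce. The check is to apply the rules as written to simple records, then ask how often they are triggered.

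**1. Records run through the rules.** The dates are constructed, with first dose on 20 June.

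| Record | Known start | Known end | Imputed start | Class under the SAP | Correct class |
|---|---|---|---|---|---|
| Adverse event | June, day unknown | 18 June | 20 June | Treatment-emergent | Not treatment-emergent |
| Antibiotic | June, day unknown (true start 8 June) | 15 June | 20 June | Concomitant | Prior |

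In both rows the imputed start is later than the recorded end. The out-of-order row in Table 6 does not act, because the end date is complete and not estimated. Where the end is itself estimated, for example known only to a month before the first-dose month while the start is known only to the year, that row pushes the end past the imputed first-dose start. The one clue that the event was over before dosing is then lost.

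**2. How often a partial start triggers the rule.** Take first-dose dates spread evenly over a 365-day year and a true start k days before dosing.

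- *Day missing.* The start falls in an earlier month only if dosing is in the first k days of one of the 12 months. The share caught is (365 − 12k)/365:
  - k = 1: 353/365 = 96.7%
  - k = 7: 281/365 = 77.0%
  - mean over k = 1 to 7: (365 − 12 × 4)/365 = 317/365 = 86.8%
  - k = 10: 245/365 = 67.1%
  - k = 14: 197/365 = 54.0%
- *Month and day missing.* The share caught is (365 − k)/365: 99.7% at k = 1 and 96.2% at k = 14.
- *Whole date missing.* The rule always applies.

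If the start month is known and precedes the first-dose month, both tables impute the first of that month, and a record with a known pre-dose end is classified correctly.

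These shares are conditional on a record that already has a partial start and a known pre-dose end. They do not say how many such records exist.

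**3. Illustration of scale, on assumptions only.** The documents give neither the share of infants with a pre-dose antibiotic course nor the rate of missing start days. Suppose 60% to 90% of the 396 infants had one such course, 2% to 10% of courses lacked the start day, and 67% to 84% of those starts fell in the first-dose month (about 10 and 5 days before dosing):

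- Low: 396 × 0.60 × 0.02 × 0.67 = 3.2 infants
- High: 396 × 0.90 × 0.10 × 0.84 = 29.9 infants

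This range, about 3 to 30, only reflects the assumed inputs. It leaves out wholly missing starts. It also counts misfiled courses and not changed flags: an infant with genuine antibiotic or probiotic use after dosing is flagged in any case.

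**4. Effect of the repair.** With the imputed start capped at the known end date, the adverse event in step 1 is no longer treatment-emergent and the antibiotic course is prior.

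**The case against.** The strongest reply is that treating uncertain starts as treatment-emergent is a conventional conservative default, that few records will be affected, and that nothing important depends on them. Much of this stands.

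- **The default is reasonable where the timing is uncertain.** It is not where the end date is known to precede the first dose, since no uncertainty about classification remains.
- **The adverse event half is narrow.** A reader might infer that the illness behind the admission will fill the treatment-emergent tables. The documents do not support that. Protocol 8.3.1 and SAP 11.2.3 send conditions present up to and during screening to medical history, whose partial dates are not imputed. Only new events between consent and first dose are exposed. That window is at most 7 days and vanishes when screening is done on Day 1. The infants are inpatients then, and Protocol 8.3 allows dates to be taken from hospital records.
- **The prior-antibiotic subgroup is not shown to be affected.** A reader might infer that infants are moved out of it. SAP 11.3 ties the drug-code derivation only to the concomitant subgroup, and SAP 11.2 lists a separate yes/no baseline item on antibiotics in the preceding 30 days that could supply the prior one.
- **The consequences are limited.** The primary and key secondary models (SAP 11.5.2.1 and 11.5.3.1) use neither flag. The efficacy subgroup summaries of WAZ and re-hospitalization are optional. The confounder enters the sensitivity model only at p < 0.2. Listings show dates as reported, so a pre-dose end date stays visible.

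None of this corrects the classification in the tables. No other section overrides an imputed start that falls after a known end.

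**Conclusion.** The rule is wrong as written, but the fault is minor. For any record with a known pre-dose end and a start that is wholly missing, or partial in the first-dose month or year, Appendix 2 gives the wrong class. The medication table carries most of the weight, because completed pre-dose antibiotic courses are the expected pattern in this trial.

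The number of affected records cannot be stated from the documents. The range of about 3 to 30 infants is an illustration and not an estimate. The rule is the same in both arms and the records arise before dosing, so the misclassification is non-differential. It adds noise to the concomitant medication and treatment-emergent event tables, to the antibiotic/probiotic subgroup and to one sensitivity model. A reader might infer a bias in favour of one arm or a threat to the primary result; neither follows.

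**What to change.** Add a first condition to the start-date rows of both tables:

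> If the known end date (complete, or by its known month and year) is before the first dose, the imputed start may not be later than that end date. The adverse event is then not treatment-emergent; the medication is prior. The first-dose imputation, or the assumption of treatment emergence, applies only when the end date is missing, ongoing, or could fall on or after the first dose.

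This check should run before the Table 6 row that moves an estimated end date, so that an imputed start no longer pushes a pre-dose end forward.

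The cost is one line in each table and a small programming change, best made before unblinding. It needs no new data and alters neither the sample size, power nor alpha. The conservative default is kept for every record that cannot be shown to have ended before dosing.

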Appendix 3. Summary of Efficacy Analyses

Table 8. Analyses of Efficacy Parameters

Parameter	Population	Statistical Method	Missing Data	Interpretation
CFB in WAZ	mITT	MMRM	Observed cases	Primary analysis
CFB in WAZ	PP	MMRM	Observed cases	Sensitivity
CFB in WAZ	mITT, PP	MMRM adjusted for study intervention compliance	Observed cases	Secondary/Sensitivity
CFB in WAZ	mITT	MMRM with adjustment of confounding variables	Observed Cases	Secondary, Sensitivity
CFB in WAZ adjusted for gestational age	mITT	MMRM	Observed Cases	Sensitivity
CFB in Weight	mITT	MMRM	Observed cases	Key Secondary
Proportion of participants with increase in WAZ \geq 0.3, 0.4, 0.5 at Day 56	Safety, PP	Estimation of proportions with mid-P CIs and logbinomial regression to estimate risk ratio	Observed cases	Secondary, Sensitivity
Proportion of participants with WAZ > - 2	Safety, PP	Estimation of proportions with mid-P CIs and log-binomial regression to estimate risk ratio	Observed cases	Secondary, Sensitivity
Proportion of participants that were rehospitalized	Safety, PP	Neg-binomial model to estimate incidence rate ratio	Observed cases	Secondary, Sensitivity
Proportion of participants that were re-hospitalized	Safety, PP	Estimation of proportions with mid-P CIs and log-binomial model to estimate risk ratio	Observed cases	Secondary, Sensitivity

[figure not shown]
Confidential Page 48 of 50

Proportion of mITT, PP participants that had samples with presence of *B. infantis*

Estimation of proportions with mid-P CIs

Observed cases

[figure not shown]
Secondary, Sensitivity

[figure not shown]

Confidential Page 49 of 50

Page 50 of 50 Confidential

GF0015-MNK01-301 SAP

Gates MRI MNK01-301 SAP Vault eTMF Document Number: VV-TMF-47158 | 1.0

Signature Page for VV-TMF-47158 v1.0

Reason for signing: Approved	Name: Role: Biostatistics Date of signature: 15-Sep-2023 11:21:55 GMT+0000
Reason for signing: Approved	Name: Role: Clinical Development Date of signature: 15-Sep-2023 12:29:06 GMT+0000
Reason for signing: Approved	Name: Role: Biostatistics Date of signature: 15-Sep-2023 13:59:21 GMT+0000

Signature Page for VV-TMF-47158 v1.0
